9.1 Inclusion Criteria

Patients will only be eligible to participate in the study if they meet the following inclusion criteria:

1. Adult ≥ 18 years of age.
2. Diagnosis of Gaucher disease type 1 with deficient GCase enzyme activity $\leq 30\%$ of normal in leukocytes at diagnosis.
3. All female patients of childbearing potential must not be lactating and must have a negative serum pregnancy test at screening and confirmed negative by urine testing prior to dosing on Day 1.
4. Female patients of childbearing potential and male patients must be willing to follow protocol guidelines for barrier protection/contraception.
5. Able to give full informed consent for the trial.

Part 1 only: previously treated patients:

6. Treatment status at screening (screening period is 16 weeks):

Treated with either enzyme replacement therapy (ERT) or substrate reduction therapy (SRT) and started this treatment at least 2 years prior to dosing with no change in regimen for the prior 3 months. ERT dose ≥ 15 U/kg and ≤ 60 U/kg every other week.

Part 2 only: previously untreated (naïve i.e., never received ERT/SRT) patients:

7. Haemoglobin (Hb) level ≥ 1 g/dL below the lower limit of normal adjusted for age and sex, and at least one of the following at screening:
 - a. Platelet count $< 120,000/\text{mm}^3$.
 - b. Hepatomegaly on abdominal magnetic resonance imaging (MRI).
 - c. Splenomegaly on abdominal MRI.

9.2 Exclusion Criteria

Patients will not be eligible to participate in the study if they meet any of the following exclusion criteria:

1. Diagnosed or suspected type 2 or type 3 Gaucher disease (including any patient with eye movement abnormality on clinical examination).
2. Positive for neutralising antibodies to AAVS3 at screening.
3. Evidence of significant and persistent liver dysfunction at Screening defined as > 1.5 x upper limit of normal (ULN) in alanine aminotransferase (ALT), aspartate aminotransferase (AST) or total bilirubin.
4. Evidence of any of the following at screening:
 - a. Hb < 8 g/dL.

- b. Platelets $<45,000/\text{mm}^3$.
 - c. Pulmonary hypertension.
 - d. New osteonecrosis within 12 months of screening.
 - e. Fragility fracture or bone crisis within 12 months of screening.
5. Hepatitis B surface antigen (HBsAg) positive at screening.
 6. Hepatitis C antibody (Hep C Ab) positive and hepatitis C RNA polymerase chain reaction (PCR) (as follow-up test if Hep C Ab-positive)-positive at screening.
 7. Cytomegalovirus (CMV) immunoglobulin G (IgG) and CMV DNA PCR-positive at screening.
 8. Human immunodeficiency virus (HIV)-1 or -2 antibody positive at screening.
 9. Receipt of live attenuated vaccination within 12 weeks prior to screening or intends to receive such vaccination during the study.
 10. History of clinically-advanced liver disease e.g., cirrhosis, portal hypertension.
 11. History of bone marrow transplant.
 12. History of splenectomy (partial or total).
 13. History of splenic infarct within 12 months of screening.
 14. History of receiving any gene transfer medicinal product.
 15. History of receiving any investigational therapy for Gaucher disease within 60 days of screening.
 16. Participation in any other clinical study of an investigational medicinal product (IMP), and/or receiving any other IMP during the study.
 17. History of idiopathic thrombocytopaenic purpura, thrombotic thrombocytopaenic purpura, thrombocytopaenia, anaemia, hepatomegaly, splenomegaly, and/or osteoporosis, unrelated to Gaucher disease.
 18. History of, or active neoplastic disease within 5 years of screening (except for basal or squamous cell carcinoma of the skin or carcinoma in situ which has been definitively treated).
 19. History of uncontrolled cardiac failure, unstable angina, or myocardial infarction or other acute cardiac conditions requiring clinical management in the past 6 months.
 20. History of acute myocarditis or presence of acute myocarditis during screening.
 21. History of substance abuse, including alcohol abuse or alcohol dependence.
 22. Known or suspected intolerance, hypersensitivity or contraindication to the investigational medicinal product (IMP) and non-investigational medicinal products (NIMPs) or their excipients.
 23. History of anaphylaxis or infusion related reactions to ERT.
 24. Contraindication(s) to MRI. (e.g., ferromagnetic metallic implants, some types of pacing and defibrillator devices, nerve stimulators).
 25. Any clinical condition (medical or psychiatric) that, in the opinion of the investigator, could jeopardise safety or compromise ability of the patient to participate in this study.

9.3 Restrictions on Participants

9.3.1 Contraception

Male subjects must practice a reliable barrier method of contraception, until the results from three consecutive negative semen samples taken at separate visits (at least 1 week apart) after FLT201 administration are negative.

Semen samples may be omitted at the discretion of the investigator for religious or other personal reasons expressed by the subject. If the subject does not provide semen samples, barrier contraception must be continued until the results from three consecutive serum samples taken at separate visits (at least 1 week apart) after FLT201 administration are negative. In programs to date with our proprietary capsid and in the literature, semen samples become negative before serum samples.

Subjects must refrain from sperm donation for the duration of the trial.

Female participants of childbearing potential must be willing and able to use highly effective birth control methods until the results from three consecutive serum samples taken at separate visits (at least 1 week apart) after FLT201 administration are negative.

Highly effective methods of birth control are methods that achieve failure rate of less than 1% per year when used consistently and correctly:

- Combined (oestrogen- and progesterone- containing) hormonal contraception (oral, implant, injectable) associated with inhibition of ovulation (which must be stable for at least 1 full month prior to screening).
- Progesterone-only hormonal contraceptives (oral, implant, injectable) associated with inhibition of ovulation (which must be stable for at least 1 full month prior to screening).
- Progesterone-releasing intrauterine systems or the copper intrauterine device.
- Vasectomized partner.

Female participants not agreeing to use birth control must be of non-childbearing potential, defined as:

- Postmenopausal for at least 1 year before screening.
- Permanently sterilised (e.g., bilateral tubal occlusion, hysterectomy, bilateral salpingectomy).
- Or congenitally sterile.

9.3.2 Alcohol

Participants will be advised to moderate their intake of alcohol during the study and, specifically, to abstain from alcohol from 1 week prior to vector infusion and for approximately 3 months following vector infusion.

9.3.3 Other

Participants should be up to date with local vaccination policy (e.g., seasonal flu, COVID-19 vaccination).

10 Investigational Medicinal Products and Non-investigational Medicinal Products

10.1 FLT201

The ATIMP in this protocol is FLT201 Solution for Infusion.

FLT201 is a replication-incompetent ss recombinant AAV vector. The vector is composed of a ss DNA genome packaged in an AAV-derived protein capsid (see Section 6.2).

FLT201 drug product is supplied as a sterile Solution for Infusion in 10 mL Crystal Zenith® vials, each vial containing 5 mL extractable volume. The vials are sealed with rubber stoppers and aluminium seals with plastic flip tops. The product is formulated as an approximately isotonic, aqueous solution at neutral pH. The formulation also contains 0.25% w/v recombinant human albumin.

FLT201 Solution for Infusion is stored frozen at $\leq 60^{\circ}\text{C}$ until thawed for the preparation of the infusion. Detailed instructions for the preparation of infusion solutions will be provided in the FLT201 Pharmacy Manual.

The appropriate number of vials required for dosing is determined based on the weight of each participant and the allocated dose level (Day -1 weight should be used to determine the final dose).

Instructions for the preparation of FLT201 infusion solutions are also included in the FLT201 Pharmacy Manual.

10.2 Source of FLT201 Manufacture, Distribution, and Storage

10.2.1 Secondary Packaging, Labelling, and Distribution

The drug product is shipped using companies specialising in cold chain transportation of biopharmaceuticals. Vials will be packed in validated shippers for transportation and are maintained at $\leq -60^{\circ}\text{C}$ during shipment. All shipments include temperature monitoring devices so that temperature control during transit can be confirmed.

The FLT201 Solution for Infusion is supplied in single vial cartons. Vials and cartons are labelled in accordance with local regulatory requirements (for example, Annex 13 [EudraLex Volume 4] in the EU). Label text is provided in the language of each territory where dosing is to be performed, either as a multi-language booklet label or a single-panel label.

10.2.2 Infusion Sites

Administration of FLT201 will be restricted to study sites that have the capacity to store the FLT201 at the specification storage temperature and to prepare and administer the infusion solutions with the required level of control (see FLT201 Pharmacy Manual). In addition, as part of the study site selection process, the study site's ability to meet the required safety oversight of the participant will be assessed (e.g., site team emergency response capabilities/procedures and access to the required emergency response equipment/departments). If a site is not able to administer FLT201 the Sponsor will attempt to identify an alternative site for the infusion week only.

10.2.3 Receipt Storage and Handling of FLT201 at Site

All FLT201 aspects of the study at participating sites are the responsibility of the investigator, who may delegate this responsibility to the local pharmacist or other appropriately trained personnel. The delegation of duties must be documented.

Detailed instructions for the receipt, storage, and handling of FLT201 drug product are contained in the FLT201 Pharmacy Manual. All local requirements related to activities involving genetically modified organisms are adhered to.

10.2.4 Accountability and Traceability of FLT201

There is a system set-up to ensure the traceability of FLT201 from the starting material, through to administration to the participant and destruction or final transfer. A comprehensive FLT201 Pharmacy Manual and associated Standard Operating Procedures and forms are in place to ensure that the required accountability and traceability data is collected and retained. The requirement for the manufacturer and investigator/clinical study site(s) to retain their part of the traceability information is set out in the relevant contractual agreements with the Sponsor.

10.3 Name and Description of Non-investigational Medicinal Products

Prednisolone or prednisone, methylprednisolone and prolonged-release tacrolimus are NIMPs in this study. Prednisolone/prednisone, methylprednisolone, and tacrolimus will be sourced from commercial supply to the study sites. Prednisolone and prednisone are used in the same manner and are equally effective. Therefore, the recommended schedule for prednisolone, equally applies to prednisone. Tacrolimus has a narrow therapeutic index and should be prescribed by brand name to avoid inadvertent switching, and different oral formulations of tacrolimus should not be substituted during the study. Please refer to the Clinical Immune Management Plan (CIMP) and Non-investigational Medicinal Product guidelines for administration details.

Investigational sites are responsible for maintaining a system which allows adequate reconstruction of NIMP movements and evaluation of participant compliance.

Risks associated with use of NIMP as described in their Summary of Product Characteristics (SmPC) or other applicable labelling should be communicated to the participants by the investigator.

The usage of immunosuppression should be recorded in the electronic case report form (eCRF) on the 'Immunosuppressant Log'. These details include daily dosage and trough tacrolimus levels.

10.4 Immunosuppression Management

As noted in Section 6.5.3.1, liver-directed gene therapy with an AAV-based capsid has been reported to be associated with a likely T-cell mediated immune response to vector-transduced hepatocytes resulting in rises in liver transaminase levels, most notably ALT.

For all participants, LFTs will be closely monitored (Section 12.2.1) to enable timely identification and treatment of episodes of breakthrough ALT increase to preserve GCase expression (activity and concentration).

Participants will receive a prophylaxis regimen (post-dosing with FLT201) starting at approximately Week 3 post-dosing, continuing for a duration of up to approximately 3 weeks at the initial dose followed by a taper over 11 to 13 weeks.

The prophylaxis regimen consists of oral steroid (prednisolone/prednisone) and/or oral tacrolimus. An appropriate quantity of steroid and/or tacrolimus will be dispensed to the participant to cover the period between clinic visits and usage will be monitored via tablet counts.

In the event of breakthrough elevation of liver transaminase, participants will be assessed by the treating physician, and a reactive regimen (consisting of IV methylprednisolone) may be initiated in accordance with the CIMP.

The CIMP provides detail of the prophylaxis and reactive regimens, as well as more detailed guidance regarding the assessment and management in case of observed ALT elevation. The CIMP will be available to the investigator, pharmacy, and key study personnel. If the investigator considers that any systemic immune-modifying medication other than those prescribed in accordance with the CIMP may be necessary, this should be discussed with the Medical Monitor and Sponsor.

Any significant changes in the CIMP will be reviewed by the DMC, and changes may be issued as an update to the CIMP and communicated to all sites. If the DMC considers that significant changes are required, such as addition of other drugs (i.e., additional NIMP), then a protocol amendment may also be submitted.

11 Concomitant Medication

All non-study treatment received within 30 days prior to initial informed consent and for the duration of the study must be recorded on the appropriate eCRF page. Concomitant medication includes prescription and non-prescription medication and herbal treatments. Concomitant medication also includes immunosuppressants used as part of an immune management and monitoring regimen as described in the CIMP.

11.1 Gaucher Disease Therapy

Any prior use, recommencement, initiation, or discontinuation of Gaucher disease therapy, including ERT, SRT, or any other medicinal product that may impact GCase levels should be documented in the Gaucher Treatment eCRF page.

11.2 Concomitant Treatment

Concomitant treatment refers to all treatment taken between the date of investigational product infusion and the Week 38/end of study (EOS) visit, inclusive. All concomitant treatments information must be recorded on the appropriate eCRF page.

Participants should be instructed not to start taking any new medications, including non-prescription drugs and herbal preparations, unless they have received permission from the investigator, time allowing, i.e., investigator permission not required for emergency medical care. Other therapy considered necessary for the participant's welfare may be given at the discretion of the investigator. All such therapy must be recorded in the eCRF. No other ATMP/IMP may be used concomitantly with the study treatment. The participants are not allowed to participate concurrently in another clinical study.

Any systemic immune-modifying medication other than immune suppression prescribed in accordance with this protocol should be discussed with the Medical Monitor and Sponsor. Local or topical steroids, e.g., use of inhaled corticosteroids to manage chronic respiratory conditions are permitted.

In the event of an emergency, any needed medications may be prescribed without prior approval, but the Medical Monitor must be notified of the use of any excluded medications immediately thereafter.

11.3 Prior Treatment

Prior treatment includes all non-Gaucher disease therapy received from 30 days prior to the initial informed consent up until the time of FLT201 infusion. Prior treatment information must be recorded on the appropriate eCRF page.

11.3.1 Discontinuation/Resumption/Commencement of ERT/SRT

ERT/SRT will be discontinued once GCase activity is in the normal range.

If, after the discontinuation of ERT/SRT, haemoglobin or platelet levels start to decline or if disease-specific biomarkers or other clinical signs and symptoms significantly worsen compared to baseline, then ERT/SRT will be resumed. This information will then inform future decisions for subjects as to the level of GCase activity at which ERT/SRT is to be withdrawn.

In addition, GCase expression loss as evidenced by decline in serial GCase activity measurements to baseline (pre-FLT201 dosing) levels, ERT/SRT will be resumed.

The decision to withdraw or restart ERT/SRT should be discussed with the Medical Monitor and Sponsor.

12 Study Procedures

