A minimum of 4 weeks of safety/tolerability (including DLT), PK, PD, and clinical data will be assessed before dosing each participant (both within a dose cohort and before escalating to the next dose level). Four weeks post-dose approximates the time when leukocyte and plasma GCase activity levels are predicted to achieve steady state, giving an early indication of likely risk:benefit for participants at a given dose level. Any acute dose-limiting toxicities (DLT) may thus be adequately assessed in the 4 weeks post-dose period. A DLT is defined as any severe adverse event (AE) at least possibly related to FLT201 except for increases in alanine aminotransferase (ALT) or aspartate aminotransferase (AST) that are not associated with increases in bilirubin.

Dose escalation will be overseen by a DMC in accordance with the following rules:

1. Safety Assessment Based on DLT

- If 1 participant experiences a DLT, that cohort will be expanded to 3 participants.
- If 2 out of 3 participants in the same cohort experiences a DLT, the DMC will be convened to consider a dose reduction. The DLT rate is expected to be $\leq 33\%$.

2. GCase Expression

If GCase activity is below the normal range (e.g., $<1.5 \mu\text{mol/L/h}$) in the first participant in the cohort and no DLT is observed, dose escalation to the next dose cohort will occur after this first participant to avoid treating the next participant with a dose predicted to be below the therapeutic range.

3. Safety Rules Based on NOAEL

The highest dose that may be tested will not exceed 1.5×10^{13} vg/kg, which is below the no observed adverse effect level (NOAEL) of the FLT201 Good Laboratory Practice (GLP) murine toxicology study (2.57×10^{13} vg/kg).

Primary Objective	Primary Endpoints
To assess the safety and tolerability of a single IV administration of FLT201 in adults with Gaucher disease type 1 (previously treated and previously untreated)	
Primary safety endpoint:
 
 incidence of TEAEs (including DLTs) from Day 1 to the last follow-up visit 
Other safety endpoints:
 
 incidence of AEs, SAEs, and changes from baseline in vital signs, 12-lead ECG, physical examination, and laboratory assessments from Day 1 to the last follow-up
Secondary Objectives	Secondary Endpoints

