NHP plasma data supports that a dose of FLT201 at 2×10^{12} vg/kg results in plasma GCase activity in the range of 336–1308 nmol/h/mL at Day 170 post-dose (Investigator Brochure, Section 4.4.6.2).

An investigational study in Rhesus macaques (n=7) received a dose of 2×10^{12} vg/kg FLT201 (Figure 2). Plasma GCase levels increased rapidly by Day 8; some fluctuations were noted between Days 21 and 43 and levels plateaued from Day 43. The GCase plasma levels at Day 170 post-dose in this study ranged between 336 to 1308 nmol/h/mL which were consistent with GCase levels that resulted in significant and consistent substrate clearance in the *GBA*-deficient mouse study in the liver, spleen, bone marrow, and lungs. AAV2/S3 products scale well from NHP to human based on other Freeline projects and assuming linear scaling from NHP to human and taking into account the variability observed in the NHP, a dose of 4.5×10^{11} vg/kg could result in approximately 76 to 295 nmol/h/mL plasma GCase in patients. The 2×10^{12} vg/kg FLT201 dose was well tolerated in NHP with no treatment-related findings noted at the interim analysis at 6 months post-dose and is 4.4-fold greater than the proposed starting dose of FLT201 in the Phase 1/2 study.

[figure not shown]

Figure 2: Plasma GCase Activity Levels Post Single IV Infusion of FLT201 at 2×10^{12} vg/kg in Rhesus Macaques

3. Murine GLP Toxicology Data

The murine GLP toxicity study identified a NOAEL of 2.57×10^{13} vg/kg (highest dose tested) using the genome of FLT201 pseudotyped into the AAV2/8 capsid in C57bl/6 mice and is 57-fold greater than the proposed starting dose of FLT201 in the Phase 1/2 study. AAV2/8 was selected as this capsid possesses a superior ability to transduce murine hepatocytes [Nakai 2005; Gao 2002] compared to AAV2/S3 and was utilized to ensure efficient transduction to assess the impact of high vector genome levels and production of high levels of the transgene.

GCase protein. The GCase levels achieved at the NOAEL were far in excess of that expected for FLT201 in humans (>3000-fold the 250 nmol/h/mL discussed in Method 1), which would not be possible with the AAV2/S3 capsid in mice.

Using a 10x margin of safety for the NOAEL, a dose 2.57×10^{12} vg/kg using the genome of FLT201 pseudotyped into the AAV2/S3 capsid is supported by the study.

This dose does not exceed the NOAEL 2.44×10^{13} vg/kg established for the AAV2/S3 capsid safety in NHP for FLT180a in Method 4.

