8.1 Study Description

This is a first in human, Phase 1/2, open label, safety, tolerability, and efficacy study in adult patients with Gaucher disease type 1.

Participants will undergo the screening assessments described in Section 12.1.1 and Section 12.1.2. for up to 16 weeks prior to Study Day 1 (gene therapy infusion).

In Part 1, eligible participants currently receiving ERT/SRT will maintain their current treatment until a minimum of 2 consecutive results at least 4 weeks post-dosing show leukocyte GCase activity level higher than pre-dose trough GCase activity level, after which ERT/SRT may be withdrawn.

Progression from Part 1 to Part 2 will be by a substantial protocol amendment, based on safety/tolerability (including DLT), PK, PD, and clinical data.

In Part 2, eligible participants will be PUPs. Participants may need to be considered for initiation of ERT/SRT in case of a lack of a trend to normalisation in leukocyte GCase activity level in serial measurements from at least 4 weeks post-dosing, suggestive of low probability of clinical efficacy.

Treatment-eligible participants will report to the infusion study site on the day prior to receiving the gene therapy infusion (Day -1). Participants will either attend their local study site if it has been approved for FLT201 infusion, or if not, an alternative approved infusion study site. On Day 1, FLT201 will be administered as a single-dose, slow IV infusion into a peripheral vein, and the participant will remain in the study centre for at least 8 hours until the investigator has deemed the participant as fit to be discharged.

Participants will be required to undergo study evaluations at intervals over the 9-month post -treatment period. These will take place either at the study infusion site or at their local study site.

The study will be conducted in 2 parts (Figure 3):

[figure not shown]

Figure 3: Study Schema

Part 1: Dose Escalation in Previously Treated Patients

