12.1.5 Post-infusion (Days +2 and +3)

The study visits procedures scheduled on Days +2 and +3 following infusion will be performed at the infusion centre where the participant received their vector infusion.

The following assessments will be conducted at each visit (or as specified):

- Physical examination.
- Vital signs (pulse, blood pressure, respiration rate, and temperature).

- 12-lead ECG on Day +2 only.
- AE and concomitant medication status.
- LFTs (local laboratory analysis).
- Blood samples to evaluate (central laboratory analysis)
 - Haematology and chemistry (including hs troponin-T and LFTs).
 - GCase activity (Day +3 only).
- Plasma, saliva, urine, stool, (and semen, male participants only) samples for PCR of vg on Day +3 only.

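### For a Part 1 participant with an in-range GCase result that is early or unconfirmed, Protocol 8.1 says keep ERT/SRT and Protocol 11.3.1 says stop it

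*Protocol*

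**What the plan says.** Protocol 8.1, on Part 1, says that "eligible participants currently receiving ERT/SRT will maintain their current treatment until a minimum of 2 consecutive results at least 4 weeks post-dosing". The rest of that sentence sets the test for those results and what follows from passing it. They must "show leukocyte GCase activity level higher than pre-dose trough GCase activity level, after which ERT/SRT may be withdrawn". Section 8.1 thus fixes the matrix, the number of results, the earliest time and the comparator, and it makes withdrawal optional.

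Protocol 11.3.1 says "ERT/SRT will be discontinued once GCase activity is in the normal range". It goes on to require resumption if haemoglobin or platelets start to fall, if biomarkers or clinical signs significantly worsen, or if GCase activity falls back to its pre-dosing level. On experience after withdrawal it adds: "This information will then inform future decisions for subjects as to the level of GCase activity at which ERT/SRT is to be withdrawn". It closes with: "The decision to withdraw or restart ERT/SRT should be discussed with the Medical Monitor and Sponsor".

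Neither section refers to the other. The SAP does not restate the rule; SAP 7.1 only summarises and lists ERT/SRT use.

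**The concern.** Part 1 participants started ERT or SRT at least two years before dosing and have been on an unchanged regimen for three months (Protocol 9.1, criterion 6). The rule decides when they come off standard therapy, so it should give one answer for a given laboratory result.

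Two statements elsewhere in the protocol show why confirmation and timing matter. The Synopsis says "Four weeks post-dose approximates the time when leukocyte and plasma GCase activity levels are predicted to achieve steady state". Section 6.5.2 reports for macaques: "Plasma GCase levels increased rapidly by Day 8; some fluctuations were noted between Days 21 and 43 and levels plateaued from Day 43". Read literally, 11.3.1 allows a stop before predicted steady state, on one value from a period in which activity may still be moving.

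There is also an analytic cost. SAP 8.3 summarises lyso-Gb1, organ volumes, haemoglobin and platelets as change from baseline by visit and cohort, and cohorts are planned at two or three participants. If withdrawal follows one rule in some participants and the other rule in others, time off therapy varies for reasons unrelated to dose.

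**Working it through.** The plan gives no figure to reproduce, so the check is to apply both rules to the same result and then to measure the gap in time.

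**Step 1: the rules side by side.**

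| Result | Section 8.1 | Section 11.3.1 | Reading |
|---|---|---|---|
| In range before Week 4 | maintain | discontinue | opposed |
| In range at Week 4, no second result yet | maintain | discontinue | opposed |
| In range later, but leukocyte pair above trough not yet obtained | maintain | discontinue | opposed |
| Two consecutive leukocyte results from Week 4, above trough, below normal | may withdraw | trigger not met | discretion, not conflict |
| Two consecutive leukocyte results from Week 4, above trough and in range | may withdraw | discontinue | compatible |

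The third row can arise because Section 12.5.2 provides for GCase in plasma, leukocytes and dried blood spot, while 11.3.1 does not say which is meant.

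**Step 2: can the opposed cases occur?** Yes. GCase activity is drawn on Day 3 (Section 12.1.5, Table 2) and weekly from Week 1 to Week 12 (Section 12.2, Table 1), while participants are still on ERT/SRT.

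**Step 3: size of the gap on scheduled draws.** Inputs are nominal visit days, with Day 3 falling 2 days after the Day 1 infusion. Ordinary ±1 day windows and laboratory turnaround are ignored for both rules. The earliest pair under 8.1 is Weeks 4 and 5, so its earliest withdrawal is 35 days post-dose. For a draw t days post-dose, the gap is 35 − t. ERT is given every 14 days (Sections 6.1 and 9.1), so a gap of g days contains between g/14 rounded down and g/14 rounded up infusions.

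| Draw | t (days) | Gap 35 − t (days) | Gap / 14 | ERT infusions |
|---|---|---|---|---|
| Day 3 | 2 | 33 | 2.36 | 2 to 3 |
| Week 1 | 7 | 28 | 2.00 | 2 |
| Week 2 | 14 | 21 | 1.50 | 1 to 2 |
| Week 3 | 21 | 14 | 1.00 | 1 |
| Week 4 | 28 | 7 | 0.50 | 0 to 1 |

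Five scheduled results per participant are therefore exposed, with a range of 7 to 33 days and 0 to 3 infusions. For SRT the days apply but the infusion count does not.

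**Step 4: sensitivity.**
- The 33-day figure needs an in-range value two days after the vector. The only onset data shown are the macaque rise by Day 8, and such a value could instead reflect a recent ERT infusion. Without Day 3 the range is 7 to 28 days and 0 to 2 infusions.
- Week 5 is the earliest withdrawal only for scheduled draws. Unscheduled visits include GCase activity (Table 1), and raised LFTs prompt additional weekly samples (Section 12.2.1). These could complete the pair sooner, although 12.2.1 describes its samples as plasma, so they count under 8.1 only if leukocytes are assayed too.

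**The case against.** The best defence is that the sections are cumulative: 8.1 sets a minimum condition and 11.3.1 the level to reach. Withdrawals are also discussed with the same Medical Monitor and Sponsor, for about 12 Part 1 participants dosed at least four weeks apart, so divergence between sites is less likely than the bare wording suggests. That softening stands. The cumulative reading is sensible, but the text does not state it: 11.3.1 is worded as a sufficient, mandatory trigger. The discussion clause gives no criterion for choosing, and the emerging-data sentence concerns only the level of activity, not matrix, confirmation or timing. The change log records a clarification of the withdrawal approach against 11.3.1 alone, which may mean that 8.1 carries older wording, but that does not establish precedence.

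It is also fair to say that 8.1 is not complete protection. Results at Weeks 4 and 5 (28 and 35 days) still lie within the Day 21 to 43 period of fluctuation seen in macaques.

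Three stronger readings are tempting, and the documents do not support them:
- *Above trough but below normal is a further contradiction.* It is not, because 8.1 only permits withdrawal there.
- *An early in-range plasma value is the expected case.* Section 6.5.2 projects 76 to 295 nmol/h/mL at the Cohort 1 dose, which is about 51 to 197 times the example limit of 1.5 µmol/L/h in 13.3.1.2 (76/1.5 and 295/1.5; the units are equivalent). But nothing says that the two figures share an assay or matrix, and the projection scales Day 170 macaque values.
- *Residual infused enzyme invalidates the withdrawal samples.* Its persistence in leukocytes is not given, 8.1 itself specifies a trough reference, and sample collection is referred to a laboratory manual that is not among these documents.

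**Conclusion.** The inconsistency is real and should be corrected. It is confined to Part 1 participants on ERT/SRT whose in-range result comes before the 8.1 condition is met. On scheduled draws that means Day 3 and Weeks 1 to 4, with a difference of 7 to 33 days and 0 to 3 ERT infusions; the realistic upper end is nearer 28 days and 2 infusions. A later in-range result is affected only if the leukocyte pair is still missing.

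The figures assume nominal visit days, a 14-day ERT cycle and no extra samples. Harm is bounded by the resumption rule and by weekly GCase and haematology to Week 12. The documents do not show that any participant was withdrawn early, and the finding should not be read as saying so.

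**What to change.** Amend 11.3.1 so that ERT/SRT is not discontinued until the 8.1 condition is met: at least two consecutive leukocyte GCase results, at least four weeks after dosing. Name leukocytes as the matrix and use the same wording in both sections.

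The threshold is the sponsor's choice, but it should be the same in both places: above the pre-dose trough, or within the normal range. Choosing the normal range keeps participants who are above trough but below normal on therapy for longer. It also needs a leukocyte limit, or a reference to where one is held, because the only numerical example (13.3.1.2) is not tied to leukocytes. Choosing the trough keeps the present 8.1 discretion. Keep the emerging-data sentence and the Medical Monitor and Sponsor discussion. If Part 1 withdrawals have already taken place, record which condition each participant met.

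The cost is amendment wording, and withdrawal up to about five weeks later (33 days) than 11.3.1 read literally. Off-therapy observation falls by the same amount. Over 38 weeks (266 days), the largest loss is 33 of the 264 days remaining after a Day 3 stop, or 12.5%; from a Week 1 stop it is 28 of 259 days, or 10.8%. The four-week interval for escalation decisions is unaffected.
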